Analyzing the isolate to library: The isolate sequencing will be interpreted by an experienced microbiologist who will be masked to all clinical, epidemiological and microbiological study information. A reference isolate will be defined initially to compare subsequent isolates to the reference isolates for mapping the clonal spread of an isolate. The genome data will be analyzed to identify single-nucleotide polymorphisms (SNPs) and insertions or deletions. Then reference isolates will be compared to subsequent isolates for mapping clonality of the isolates to define the strain relatedness, and to define any repetition of a particular strain over a given period of time. Further, we can also define if an intervention such as pulsed-xenon disrupts the repetition pattern of strains and compare it other intervention such as manual disinfection.

Statistical Analysis

Aim 1. The primary analysis will use a Poisson regression model to compare PX-UV disinfection with sham disinfection. Analysis will begin with testing for a carryover effect, but the long 6-month washout is expected to make carryover unlikely. An interim analysis for efficacy will be made after the first 12-month intervention period using an O'Brien-Flemming boundary, the trial may be halted for efficacy if a chi square statistic of 8.78 or greater is observed for the interim test ($p \leq 0.003$). With the interim analysis, the p-value for the test at end of the study will need to be 0.049 or lower to be significant. The primary regression model will include patient age, sex, race and indicator variables for co-morbid conditions. Secondary analysis will summarize and compare study arms (and periods) on: administered antibiotic doses and types, hand hygiene compliance, room cleanliness quality (monitoring through fluorescent marking) and eiHAI colonization pressure.

Aim 2 The frequencies of genetically identical strains of eiHAIs in the selected units will be summarized descriptively with regards to timing, location and clinical strain characteristics.

Study Timeline

ACTIVITY TO ADDRESS STUDY AIMS	Year 1				Year 2				Year 3				Year 4				Year 5	
Quarter	1	2	3	4	1	2	3	4	1	2	3	4	1	2	3	4	1	2
IRB, training of environmental services staff	X	X	X	X		X				X				X				X
Phase 1 of crossover			X	X	X	X												
Wash-out period							X	X										
Phase 2 of crossover									X	X	X	X						
Laboratory analysis						X	X	X					X	X	X			
Data analysis and manuscript preparation									X	X	X			X	X	X	X	X

Potential Problems, Alternative Strategies, and Benchmarks for Success

While not anticipated, delays in the intervention could occur due to staffing and other logistical issues. Based on the experience of current customers of the PX-UV system, we do not anticipate a disruption to the workflow and patient through-put on the study units, but such a disruption could impact compliance with the use of the PX-UV devices. We have safeguarded against these potential issues, by garnering the full support of Detroit Medical Center, Xenex and the environmental services company, Sodexo. We have budgeted for the time and effort of Sodexo employees to carry out the PX-UV intervention. We do not anticipate any problems with laboratory aspects of the project because of the use of standardized methods in an experienced laboratory.

The benchmarks for success are: (1) the successful operationalization of the intervention (both PX-UV devices and sham controls) without disruption of patient flow; (2) maintaining routine, objective measurements of hand hygiene and room disinfection throughout the study period; (3) the reduction of both the rate of eiHAs and the recovery of genetically identical strains of drug resistant organisms on study units; and (4) development of an automatic, replicable and scalable intervention to reduce the risk of *C. difficile* and other eiHAs.

Protection of Human Subjects

1. Risks to the Subjects

a. Human Subjects Involvement and Characteristics

The human subjects involved in this study will be cared for on units where either PX-UV or sham unit disinfection occurs following each patient discharge. The room disinfection will only occur when the room is unoccupied, so there is no direct risk to the patient from PX-UV disinfection treatments. The medical treatment that patients receive will not be impacted in any way by this study and the patients will not undergo any additional testing as a result of participating in the study. We anticipate that 40,852 human subjects will participate in the study. The anticipated age range is 18-100 years. All patients will be hospitalized on study units.

The criteria for inclusion in the study is admission to the study units. Only patients who remain in the hospital for four calendar days or longer will be eligible for evaluation of eiHAI outcomes (the day of admission counts as calendar day one). Patients who do not develop an eiHAI at the time of unit discharge will be eligible for eiHAI outcomes for up to calendar 3 days following unit discharge.

Rationale for the involvement of special classes of subjects: Fetuses, neonates and children will not be included because they are not cared for on the types of units where the study is being performed.

Prisoners, institutionalized individuals and others who may be reasonably believed to be vulnerable populations will be enrolled in the study because the study presents no more than minimal risk and no more than inconvenience to the participants. In addition, it would not be practical to exclude these populations without adversely effecting the study's impact and objectives. These subjects are not the primary focus of this research study.

Pregnant women will be enrolled in the study if they meet the inclusion criteria specified above and also in the Research Strategy. These subjects are not the primary focus of this research study.

Collaborating sites where human subjects research will be performed are listed below. Investigators at these sites will be responsible for enrolling patients and collecting the appropriate samples and data. Collaborating sites are:

- Detroit Receiving Hospital, Detroit, MI, USA
- Sinai Grace Hospital, Detroit, MI, USA
-

b. Sources of Materials

No research material will be obtained from living human subjects. Bacterial isolates derived from cultures taken from subjects as part of their routine clinical care will be

collected from the participating clinical microbiology laboratories.

The data recorded on human subjects involved in the project will include demographic details (age, gender, race, etc.), underlying illnesses, antibiotic use, occurrence of infections and admission and discharge dates to and from units and the hospital. The data will be collected by review of the subject's medical records. Subject identities will be known only by the study personnel at the participating centers. Study personnel include the co-investigators and study coordinator. Subject identities will not be revealed to the statistician ([name]) or to other participating centers. Subjects will be identified by a code comprising the hospital location followed by a triple digit number. This code will be linked to subject identities on a secure, password-protected computer of the Project Coordinator at Wayne State. The list linking codes to subject identity will be kept on a password-protected computer or as a paper copy in a locked filing cabinet in a locked room of the study coordinator at Wayne State.

c. Potential Risks

Risks associated with confidentiality:

We will preserve subject confidentiality by assigning a special research code number to medical record information stored. No personal identifying information will be entered in the Research Registry. Information linking the research code number to name and other personal identifiers will be stored in a separate secure location of the Project Coordinator. Access to any information contained within the Research Registry will be limited to investigators associated with the study and their research staff.

2. Adequacy of Protection against Risks

a. Recruitment and Informed Consent

All subjects admitted to study units during the study period will be enrolled. The study will request a waiver of consent.

b. Protection against Risk

Protection against loss of confidentiality of personal medical information will be by ensuring that only the clinical investigators and relevant study personnel will have access to any personal data obtained. Personal information will be kept in a locked filing cabinet or a password-protected computer within a locked room of the Project Coordinator at Wayne State. No medications or surgical interventions will be performed for the purpose of the study.

3. Potential Benefits of the Proposed Research to the Subjects and Others

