Prior research with automated disinfection systems focused on the terminal disinfection of isolation rooms only. This is a problem, as patients might be infected or colonized with an eiHAI but the eiHAI might not be detected during the hospital stay. This type of approach probably will likely “miss” certain rooms where a patient is a silent carrier of an eiHAI. This type of approach also results in a low daily use of such technologies and limits the global effect of UV disinfection on a hospital unit’s environmental hygiene. In the proposed project, the automated disinfection system (PX-UV) will be used following every discharge on participating units. This approach will significantly increase the frequency, breadth and impact of the intervention on study units in a way that has not been previously studied.

Use of sham device and double-blind status

The proposed study is also novel in its use of sham automated devices to provide a “placebo” intervention and facilitate control for many potential confounders associated with the implementation of automated disinfection devices on the study units, such as changes in general infection control awareness and practices and environmental hygiene. Additionally, all healthcare personnel (including device operators and environmental services staff), will be blinded to the intervention/sham status of the devices. In addition, the study personnel including the PI and individuals performing data analysis, will be blinded to the intervention/sham status of the devices. The device status will be written on a piece of paper by the manufacturer with the serial numbers of each device indicated, sealed in an envelope and kept in a secure location by the study statistician ([name]) for later retrieval when trial data analysis has been completed.

Use of crossover design

The crossover study design represents an improvement in study design quality compared with studies in the current literature and allows for the control of additional measured and unmeasured confounders. A crossover design, with each unit observed with both the active and sham intervention, means each unit serves as its own control, which will improve the precision of the comparison, reducing the number of units and total expense required for the study.

Notable differences from recent CDC-sponsored trial

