For the 16 units to be studied, over 8 months from December 2014 through July 2015, the average rate of *C. difficile* infections on day 4+ of a patient's hospital stay was 1.3 per 1000 days. Rates of ESBL+VRE+ MRSA + *A. baumannii* are 1.5 times that for *C. difficile*, so the total rate of all four infection types would be 3.2 (=1.3x2.5). The total average daily census on the 16 units was 291. Assuming the average patient stay is 5.2 days, 42.3% of patient days will be day 4+, so the expected number of daily eligible patient days would be 123. For 24 months of intervention the total number of eligible days would be $123 \times 730 = 89,790$, or 44,895 per arm.

If the power for the Poisson model is approximated by that for a binomial test of proportions, and with a final alpha level of 0.049 to take into account one interim analysis, a 31% reduction in eiHAI incidence (from 3.2 to 2.208 per 1000 eligible days) would be detectable with 81% power.

Hospital Unit Selection

Patient care units from two healthcare facilities have been identified for this study based on a relatively high average recovery of eiHAs. These units will be randomized to receive either the intervention or sham PX-UV devices in Phase 1 of the study, and the intervention and sham PX-UV devices will switch in Phase 2 of the study. The protocol for use of the devices is outlined below.

Clinical Sites

Two DMC acute-care hospitals are being proposed for this project, Sinai-Grace Hospital (SGH) and Detroit Receiving Hospital (DRH). SGH is a 383-bed hospital, and DRH is a 248-bed hospital. The study will be conducted in eight hospital units in SGH and eight hospital units in DRH, including two medical intensive care units (ICUs), two surgical ICUs and 12 non-ICU medical-surgical wards. The 16 study units include a total of 379 beds. During the 24-month study intervention period, we anticipate that 40,852 total patients will be cared for on study units accounting for 89,790 eligible patient days out of a total of 212,430 patient days. If past experience continues unchanged, during the 24-months of intervention, 287 eiHAs attributable to these units would be observed.

Devices will be deployed on these study units with the sham and intervention devices split evenly between SGH and DRH. Within each study site, the types of devices (PX-UV vs sham) will be assigned randomly to the units in Phase 1 and then switched in Phase 2.

Patient Selection

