- Environmental cleaning quality: monthly measures of cleaning quality using EnCompass™ Environmental Monitoring Program will be conducted by environmental services at study hospitals with a minimum of 2 room inspections marking 10-15 high-touch surfaces in a patient room with an invisible marker per unit per month (for a total of 16 inspections per month).⁴⁰ In addition, every other month, a minimum of 1 room per unit will be visually inspected but a study team member using the EnCompass™ Environmental Monitoring Program.
- Staffing levels: Average number of nurses per patient on study units.
- Frequency of eiHAI pathogens recovered within the first 72 hours of unit admission to determine eiHAI colonization pressure.
- PX-UV compliance: number of rooms receiving sham/intervention PX-UV divided by the number of discharges
- PX-UV Sham/Intervention status: this variable will be blinded to both the healthcare workers and patients on the units and to the research team.

Description of Intervention Protocol

The PX-UV devices will be placed in three positions in a standard patient room for a UV cycle time of five minutes each. An operator will move the PX-UV devices between positions. While the device is operating in the bathroom, workers can clean in the main room to save time. Before PX-UV disinfection, the room will be cleaned according to the standard terminal cleaning protocol for that room, which may include the use of sodium hypochlorite in the case of *C. difficile* isolation rooms. Between positions 2 and 3, the operator will make certain that objects, such as telephones, TV remote controls and call buttons are inverted to allow for UV exposure on all sides.

Description of sham device

For the sham units, a non-UV producing bulb has been designed that will produce a flash that will be visually and audibly indistinguishable from the flash produced by the device that creates germicidal UV. The cart and other features of both the intervention and sham devices will be indistinguishable. The study team and room cleaning staff (environmental services personnel) will be blinded to the sham/intervention status of all devices.

APPROACHES TO ADDRESS EACH SPECIFIC AIM**Aim 1:** To evaluate the impact of PX-UV disinfection on rates of eiHAIs on study units by:

- 1.1. Comparing rates of eiHAIs on study units where a) PX-UV is added to standard terminal cleaning practices to b) units where a sham UV disinfection system is added to standard terminal cleaning.

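### The Phase 1 efficacy stopping rule states no direction, is not reconciled with the sealed device key, and keeps its p of 0.003 only if event rates do not vary between units

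*Combined protocol and SAP*

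**What the plan says.** Statistical Analysis, Aim 1, sets the interim look: "An interim analysis for efficacy will be made after the first 12-month intervention period". Its rule is that "the trial may be halted for efficacy if a chi square statistic of 8.78 or greater is observed for the interim test", equated there with p of 0.003 or less. The final test is then held to 0.049. The model is a Poisson regression with patient age, sex, race and co-morbidity indicators. No term for hospital unit is listed.

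Allocation is by unit within hospital (Clinical Sites): "the types of devices (PX-UV vs sham) will be assigned randomly to the units in Phase 1 and then switched in Phase 2".

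The section on the sham device and double-blind status says that "the study personnel including the PI and individuals performing data analysis, will be blinded to the intervention/sham status of the devices". The manufacturer's list of device status by serial number is "sealed in an envelope and kept in a secure location by the study statistician", "for later retrieval when trial data analysis has been completed". The list of unit-level variables says of sham/intervention status that "this variable will be blinded to both the healthcare workers and patients on the units and to the research team".

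The documents describe no masked group code, no unblinded statistician, no monitoring committee and no opening of the envelope at the interim.

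**The concern.** There are two separate weaknesses in one decision rule.

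**Direction and blinding.** A chi-square is the same whichever arm does better. Stopping for efficacy needs to know that PX-UV is the better arm, and the only record of that is sealed until after the analysis. The blinding section makes no exception for the interim, and the interim rule does not mention the blind.

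**Calibration.** The crossover makes each unit its own control only once both periods are in. After Phase 1 the comparison is between eight units on one device type and eight different units on the other. A Poisson model without a unit term treats all variation as event-count noise. If underlying rates differ between units, and the 16 units mix four ICUs with 12 wards, the standard error is too small and the boundary is crossed by chance more often than stated.

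At stake is the trial's only early-stopping decision. A false halt would lose Phase 2, and with it the within-unit comparison that the design was chosen for.

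**Working it through.** **1. The plan's own figures.** Lan-DeMets spending of O'Brien-Fleming type, two-sided 0.05, two looks, half the information at the first, gives z = 2.963, chi-square 8.777, two-sided p = 0.00305 and a final p of 0.0490. The 8.78, 0.003 and 0.049 all reproduce, and together they give an overall alpha of 0.0500. Stated power also reproduces: 3.2 versus 2.208 per 1000 eligible days, 44,895 days per arm and alpha 0.049 (two-sided assumed) give 81.4% against the stated 81%.

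**2. Symmetry.** With equal exposure, chi-square = (a − b)²/(a + b). For 72 versus 40 events this is 32²/112 = 9.14, whichever arm has the 40. Both outcomes meet the written boundary.

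**3. Size of the direction problem without unit variation.** √8.78 = 2.963, and the one-tail normal probability is 0.0015. So 0.15% of null trials cross in favour of sham and 0.15% in favour of PX-UV. If PX-UV were truly worse (assumed rate ratios 1.2, 1.3, 1.45), a sham-favouring crossing would have probability about 3.5%, 10% and 30%.

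**4. Size of the calibration problem.** Phase 1 exposure is half of 44,895, or 22,448 eligible days per arm. At 3.2 per 1000 that is 71.8 events per arm, 143.6 in all. Assumptions not in the documents: unit-rate CV from 0.2 to 0.5, and unit-size CV of 0.4.

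Approximate check by hand:
- Poisson variance of the log rate ratio: 2/71.8 = 0.0279.
- Effective units per arm: 8/(1 + 0.4²) = 6.9.
- Added variance from unit rates: 2 × CV²/6.9.
- Inflation D = 1 + added variance/0.0279. The true null crossing rate is the two-sided normal tail beyond 2.963/√D.

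| Unit-rate CV | D | 2.963/√D | Crossing, by hand | Crossing, simulated |
|---|---|---|---|---|
| 0 | 1.00 | 2.96 | 0.3% | 0.2–0.3% |
| 0.2 | 1.42 | 2.49 | 1.3% | 1.1% |
| 0.3 | 1.94 | 2.13 | 3.3% | 2.8% |
| 0.4 | 2.67 | 1.81 | 7.0% | 6.1% |
| 0.5 | 3.60 | 1.56 | 11.8% | 10.6% |

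The simulation uses 16 units, eight per arm, with the Poisson standard error and no patient covariates. About half of the crossings favour sham.

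**5. Does a scaled variance suffice?** Estimating the extra variance from 16 units and still using z of 2.963 gives about 0.5% to 1.1%, which remains above 0.3%. A t reference on about 14 df (16 units less two arm means) at two-sided 0.003 moves the critical value to 3.58. In a simulation with the same inputs, and the scale factor not allowed below 1, null crossings were then at most about 0.3%.

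**6. Price at the planned effect.** In the unclustered model the chance of stopping at a true 31% reduction is Φ[(0.000992 − 2.963 × 0.000490)/0.000490] = Φ(−0.94), about 17%. With the t reference, simulation under the same assumptions puts it at roughly 2% to 4%.

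**The case against.** A reader might infer that the interim cannot be run at all. The documents do not support that: a symmetric statistic can be computed on two masked groups with the envelope closed. Such codes are not described, so this is a gap in specification and not an impossibility.

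A reader might also infer a forced choice between stopping without knowing the direction and running Phase 2 with an unblinded statistician. That does not follow either. If the boundary is not crossed, nothing need be opened. If it is crossed in favour of PX-UV and the trial halts, there is no Phase 2 to compromise. Only a sham-favouring crossing, or a decision to continue after crossing, leaves Phase 2 running after the key is known. Operators and cleaning staff would stay blinded, and outcomes are laboratory PCR and culture results.

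The word efficacy, read with the central hypothesis, implies PX-UV is better, and the rule permits a halt without requiring one. A sensible team would be unlikely to declare efficacy for sham. All of this stands, and it reduces the direction point to one of wording.

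On calibration, the CVs are assumed, and patient covariates may absorb some of the unit differences. That too stands: what matters is the variation left after adjustment, which is unknown. It does not remove the point, because the plan offers no unit term and no reason to take residual variation as zero. The inflation comes from clustering, so settling the blinding question would not cure it.

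**Conclusion.** The concern holds in two parts. First, the interim rule states no direction and is not reconciled with the sealed key. The rule can be run, but a halt for efficacy cannot be confirmed under the plan as written. With no unit variation, the probability at stake under the null is about 0.15%. Second, and more important in size, the stated p of 0.003 is correct only if unit rates do not vary. For assumed residual unit-rate CVs of 0.2 to 0.5 and a unit-size CV of 0.4, the null crossing rate is about 1% to 11%, about half favouring sham. The boundary values 8.78 and 0.049 are not themselves in error. This should be corrected before the interim look.

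**What to change.** 1. In Statistical Analysis, Aim 1, state that stopping for efficacy requires the lower event rate under PX-UV as well as p of 0.003 or less. The 8.78 and 0.049 are unchanged, and nothing is lost.
2. Compute the interim test with a variance that reflects variation between units, and refer it to a small-sample distribution, for example t on about 14 df at two-sided 0.003. Keeping z of 2.963 with a scaled variance is not enough.
3. Reconcile the blinding section with the interim rule: the interim is run on masked group codes, and the envelope is opened only if the boundary is crossed, by someone who does no study analysis.

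Items 1 and 3 cost a few sentences and the naming of one person. Item 2 needs no extra data, but it lowers the chance of stopping early below the 17% or so of the unclustered model, to the order of 2% to 4% under the assumptions above.

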OBJECTIVE: To conduct a prospective, sham controlled, double-blinded, interventional crossover trial to compare standard terminal cleaning plus sham PX-UV (control) with standard terminal cleaning plus PX-UV (intervention) with crossover at 12 months, following a 6-month washout period. Outcome measures include the rates of eiHAIs, as well as the recurrence of genetically identical strains of eiHAIs in patients on study units. The study will be conducted in 2 hospitals and 16 hospital units consisting of a total of 379 beds. A total of three PX-UV devices and three sham devices will be used as part of terminal cleaning following each discharge on study units.

Our central hypothesis is that the addition of PX-UV to standard terminal cleaning will be associated with superior infection prevention, resulting in a reduction in the rate of eiHAIs, as well as a reduction in the recovery of genetically identical strains of drug-resistant organisms. **At the conclusion of the proposed project**, novel data will be generated from a rigorously controlled study regarding the effectiveness of PX-UV in reducing eiHAIs in a representative healthcare setting.

Aim 1: To evaluate the impact of PX-UV disinfection on rates of eiHAIs on study units by:

- 1.1. Comparing rates of eiHAIs on a) study units where PX-UV is added to standard terminal cleaning practices to b) units where a sham UV disinfection system is added to standard terminal cleaning.
- 1.2. Comparing Rates of eiHAIs on the same medical ward during each of two 12-month phases of a crossover study (one phase when a PX-UV device is added and one when a sham device is added to standard terminal cleaning).

Method 1: PX-UV Devices will be used following each discharge on study units, with intervention devices emitting germicidal UV on 50% of the units and sham devices not emitting germicidal UV on 50% of the units, with device users and the study team blinded to the device's sham/intervention status. Rates of eiHAIs will be the primary outcome. Other key variables to be evaluated will include: types and quantities of antibiotics administered, hand hygiene compliance, room cleanliness quality monitoring through fluorescent marking, colonization pressure on study units; and co-morbid conditions and demographics of enrolled patients.

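### Units are randomised within hospital, but the primary model omits hospital, unit and phase, so hospital-specific changes between phases add unmodelled variation to the PX-UV rate ratio

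*Combined protocol and SAP*

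**What the plan says.** The Clinical Sites section places the study in "eight hospital units in SGH and eight hospital units in DRH", a mix of 4 ICUs and 12 wards, and sets the allocation: "Within each study site, the types of devices (PX-UV vs sham) will be assigned randomly to the units in Phase 1", with every unit switching in Phase 2. The same section has "sham and intervention devices split evenly between SGH and DRH". Method 1 under Aim 1 puts "sham devices not emitting germicidal UV on 50% of the units", so the overall ratio is 8:8. The Objective provides "three PX-UV devices and three sham devices". The number of units per sequence inside each hospital is not stated, and nothing balances unit type, unit size or eligible days.

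The Statistical Analysis section, Aim 1, gives the only outcome model: "The primary analysis will use a Poisson regression model to compare PX-UV disinfection with sham disinfection". On its terms it says: "The primary regression model will include patient age, sex, race and indicator variables for co-morbid conditions". It names no hospital, unit, phase or hospital-by-phase term. The secondary analysis compares arms and periods on process measures, not eiHAI by hospital. The crossover rationale says that each unit acts as its own control, but no model term carries that out.

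**The concern.** The factor that restricts the randomisation is missing from the analysis. The two 12-month phases are separated by a 6-month washout, so the comparison spans 30 months in two hospitals. An outbreak, or a change of practice in one hospital only, would alter that hospital's rate between phases. Unit effects remove fixed differences between units. A common phase effect removes a change shared by both hospitals. Neither removes a change that differs by hospital.

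Any such change is divided between PX-UV and sham according to how each hospital's expected events fall between the two sequences. If the split is unequal, the arms receive unequal shares, and the model-based standard error does not allow for it. At stake is the actual size of the final 0.049 test. At the Phase 1 interim look no unit has crossed over, so even a constant difference between the hospitals remains in a comparison that can stop the trial.

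**Working it through.** **1. The plan's own power.** Inputs from Sample size estimation: 44,895 eligible days per arm, 3.2 against 2.208 per 1,000, alpha 0.049 (two-sided, z = 1.969). The two-proportion formula gives 81.4%, matching the stated 81%. Expected events are 44,895 × 0.0032 = 143.7 and 44,895 × 0.002208 = 99.1. The standard error of the log rate ratio is √(1/143.7 + 1/99.1) = 0.131 under the planned effect, and √(2/143.7) = 0.118 under no effect.

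**2. How the leak arises.** Take two hospitals of equal size, a true rate ratio of 1 and a Phase 1 rate of 1 in both. Let a share *f* of hospital A's days, and 1 − *f* of hospital B's, be in the sequence that starts on PX-UV. Each arm has 2 units of days in total. Suppose A's rate is multiplied by 0.7 in Phase 2 and B's by 1.3.
- *f* = 0.5: the rate ratio is exactly 1.000.
- *f* = 0.6: PX-UV events 0.6 + 0.4×0.7 + 0.4 + 0.6×1.3 = 2.06; sham events 0.4 + 0.6×0.7 + 0.6 + 0.4×1.3 = 1.94; ratio 1.062.
- *f* = 0.625 (5:3 and 3:5 units of equal size): 2.075/1.925 = 1.078.

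If only A changes, the last two become 1.88/1.82 = 1.033 and 1.8875/1.8125 = 1.041. In all four unbalanced cases a hospital main effect, a common phase effect, or both together leave the leak essentially in place (for example 1.036 with both, against 1.033). Hospital-by-phase returns the ratio to 1.000, because the arms are then compared inside each hospital and phase.

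**3. Size over random allocations.** The imbalance is a matter of chance. With 4:4 allocation in each hospital, a unit-size coefficient of variation of 0.2 to 0.5, and either a 30% fall in one hospital or opposite 30% changes, the leaked log rate ratio has mean 0.000 and SD 0.011 to 0.036.

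A fuller simulation assumed 2 ICUs of 10–16 beds and 6 larger wards per hospital, 379 beds in all, a unit-rate coefficient of variation of 0.4, Poisson counts, and unit and common phase effects already fitted:

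| Phase 2 multipliers | SD of log-ratio shift | False positives without hospital-by-phase | With it |
|---|---|---|---|
| ×0.80 / ×1.25 | about 0.03 | 5.5–5.6% | 4.9–5.1% |
| ×0.67 / ×1.5 | about 0.05 | 7.1–7.4% | 4.7–5.2% |

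Ranges are over repeated runs. A comparison with no unit or phase term, closest to the model as written, gave 5.6% and 7.3%.

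A hand check agrees. Treat the shift as extra variance, so that the false-positive rate is 2Φ(−1.969 × 0.118/√(0.118² + s²)). With s = 0.03 this is 2Φ(−1.908) = 5.6%; with s = 0.05 it is 2Φ(−1.813) = 7.0%.

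**4. Interim look.** At half the events (71.8 per arm) the null standard error is √(2/71.8) = 0.167. If the hospitals differ 1.5-fold to 2-fold (assumed), imbalance in exposure shifts the log ratio with SD 0.034 to 0.058 when hospital is not in the model. The boundary of 8.78 is z = 2.963, nominal p = 0.0030. The same variance argument gives 2Φ(−2.963 × 0.167/√(0.167² + s²)) = 0.0037 to 0.0051.

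**5. Power cost of the term.** The variance is inflated by 1/(1 − (2*f* − 1)²). At *f* = 0.5 the factor is 1 and power stays 81.4%. At 0.6 it is 1.042 and power is 79.8%. At 0.625 it is 1.067 and power is 78.9%. In the 4:4 simulations with equal hospital trends, power fell by 0.3 to 0.6 points (for example from 80.7% to 80.1%).

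**The case against.** A reader might infer that leaving hospital out biases the PX-UV estimate. The documents do not support that. Allocation is random within hospital, half the units start on each device type, and every unit switches. If expected events are balanced between sequences within each hospital, the leak is exactly zero whatever the hospitals' sizes, rates or trends. Otherwise it is as likely to favour PX-UV as sham. This objection stands in full.

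A reader might also infer that diverging trends are likely. The documents point, if anything, the other way: one medical director oversees infection control at both hospitals, one health system and one environmental services company are involved, and a single PCR method for *C. difficile* is described. The multipliers used here are 1.6-fold and 2.25-fold divergences chosen for illustration, and the milder one moves the test size hardly at all. Unit-level process measures could reveal divergence, although the primary model does not adjust for them.

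A third tempting reading is that adding hospital as a main effect is enough. In the final analysis it is not, and the term is redundant once fixed unit effects are fitted.

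The point survives because exact balance is not assured. The even-split sentence concerns devices, and three of each type cannot be halved over two hospitals. No 4:4 unit count per hospital is given, and ICUs and wards will differ in days and rates.

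**Conclusion.** The omission is plain in the text, but its consequence is modest and conditional. It is variation that the model ignores, centred on zero, with an SD of about a quarter to two-fifths of the planned standard error (0.03/0.13 to 0.05/0.13). Under the assumed unit sizes and opposite hospital trends, the final test's false-positive rate is about 5.5% to 7% and not about 5%. If the hospitals move together, or expected events happen to balance within each hospital, there is no effect. The sample size calculation is not in error on this point. This is a low-severity improvement, worth making because it is nearly free and follows the randomisation.

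**What to change.** In the Statistical Analysis section, Aim 1, specify that the final Poisson model contains unit, phase and hospital-by-phase terms alongside the treatment effect and the patient covariates. Unit effects absorb the hospital main effect, so it need not be listed separately. Specify that the Phase 1 interim model includes hospital. In the Clinical Sites section, state how many units in each hospital go to each sequence.

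The change is SAP wording only. Hospital-by-phase uses one degree of freedom beyond unit and phase. Power falls by about 0.5 points with 4:4 allocation in each hospital, and by up to about 2.5 points (81.4% to 78.9%) if units split 5:3, which is a further reason to fix the split in advance.
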